## **SUMMARY OF CHANGES**

For Protocol Amendment# to:

NCI Protocol #: *N*/A DF/HCC Protocol#: 17-689

NCI Version Date: Protocol Date: 11/24/2023

#	Section	Page(s)   Change				
1.		1,2,3	1,2,3 !Staffing changes			
2.		4,8,11,12	9,8,11,12         Scientific changes, decrease in prospective recruitment			
3.						
4.						
5.						

Statistician: [name] BIDMC [contact]

# Study Exempt from IND Requirements per 21 CFR 312.2(b).

## SCHEMA

[figure not shown]
#### Figure 1. Reader Study

Prospectively acquired imaging sets will be added to existing cases for the case collection. Types of cases and the number of cases to be recruited are presented. Cases to be used for the reader study are shaded green.

### Figure 2. Prospective Case Collection

Additional images for the reader study will be prospectively recruited. These patients will be recruited prior to receiving breast biopsy (shaded green) based on a finding initially seen on screening mammography.

# **1. OBJECTIVES**

The objective of this study is to show the Contrast Enhanced Spectral Mammography (CESM) is non-inferior to breast MRI (complete and abbreviated protocols) for breast cancer screening.

### 1.1 Study Design

This study is a multi-reader, multi-case (MRMC) enriched reader study that will be performed over two years using imaging sets of CESM and breast MRI collected from a screening population.

### 1.1.1 Case Selection for the Reader Study

Cases to be included will be categorized as negative, biopsy proven benign, and biopsy proven malignant. The total number of cases required for each group can be seen in Figure 3.

Cases needed for reader study	Total # of cases needed for reader study			
Negative/ Biopsy Proven Benign	88			
Biopsy Proven Cancer	44			
Total number of cases	132			
Figure 3. Number of negative, biopsy proven benign, and biopsy proven cancer cases. Given				
the varying proportions identified in FDA approved studies and other MRMC imaging				
evaluations, this ratio of negative/biopsy proven benign to biopsy proven cancer cases was seen				
as acceptable. [1-5]				

Of the 132 imaging sets required for the reader study, 54 were previously acquired through another research study (DF-HCC 14-225) and clinical practice. 4 of these cases were malignant. Cases acquired through DF-HCC 14-225 were incorporated into the Online Medical Record, as specified in the protocol, similar to those cases acquired for clinical practice. We are requesting a waiver of informed consent to include these imaging sets that are a part of the clinical record in the current reader study.

We will prospectively recruit the additional 40 cancers and 38 negative/benign cases necessary for the reader study. These cases will be prospectively recruited from a population of women who are undergoing biopsy in order to maximize the number of cancers identified. This will be discussed in more detail in Section 1.1.2.

Thus, the cases to be collected and used for the reader study will be broken down as demonstrated in Figure 1 of the Schema.

# 1.1.2 Prospective Image Acquisition:

CESM and MRI images will be prospectively collected to identify additional malignant and benign cases that are required for the reader study. All cases to be prospectively recruited will be selected from a population for whom a breast biopsy has been recommended based on an initial screening study, as illustrated in Figure 2. By performing the imaging prior to the biopsy, this ensures that there are no post-biopsy changes that may bias a radiologist reader during the reader study.

[figure not shown]

Figure 2. Additional images for the reader study will be prospectively recruited. These patients will be recruited prior to receiving breast biopsy (shaded green) based on a finding initially seen on screening mammography.

*Screening and enrollment:* Women will be identified at the time of their diagnostic work-up when a biopsy is recommended. If the participant meets screening requirements, informed consent will be obtained at that time and eligibility tests will be performed. Pregnancy tests will be checked on all premenopausal women and creatinine clearance (to evaluate renal function) will be checked according to the clinical protocol. If the participant meets all eligibility requirements, then she will be enrolled to the study.

To evaluate how CESM works with all types of cancer (both subtle and more obvious), patients will be recruited consecutively from BI-RADS 4A, 4B, 4C, and 5 such that there is an equal distribution among the categories. Patients will continue to be enrolled across all BI-RADS categories until the necessary number of cases with cancer has been acquired.

*Study plan:* Each enrolled participant will receive both a CESM and MRI exam *prior* to the breast biopsy. If the CESM has already been done as part of standard of care within 3 months,

then only the MRI will be performed. If the MRI has already been done as part of the standard of care within 3 months, then only the CESM will be performed. If neither has been performed already, then both exams will be performed prior to the biopsy, to occur within 3 months of each other and the biopsy.

Given that CESM and MRI are FDA approved for diagnostic imaging, and are used in our clinical practice, all CESM and MRI studies performed will be interpreted by the clinical radiology staff and clinical reports will be generated in the online medical record. The participant will be contacted by her referring physician with imaging results, per clinical practice.

There should no delay of the subsequent breast biopsy. As of now, patients receive biopsies within one week of their diagnostic imaging. This should not change with the initiation of this study. We will be performing the breast MRI on the hospital's research scanner, so we will not be limited by the clinical MRI schedule, and should be able to schedule this fairly quickly. The CESM is similar to a diagnostic mammogram and is very easy to add into the routine clinical schedule.

*Follow-up:* No dedicated follow-up research visits are necessary. However, follow-up visits per clinical care may occur, although they are rare. Given that these patients are all diagnosed with breast cancer, there is a strong attempt to address all imaging findings before treatment. In addition, given that patients will have had received both MRI and CESM, it is even less likely that there will be a finding seen on CESM that it not seen on breast MRI and addressed before treatment. As a result, there is a very small chance for a CESM only finding. If this should occur, the finding will be addressed prior to treatment, if there is a high concern for malignancy. If the likelihood of cancer is felt to be low and tissue sampling can't be performed, then a follow-up CESM may be recommended.

# 1.1.3 Case Collection and Categorization:

Prospectively acquired imaging sets of CESM and MRI will be added to existing cases that were previously acquired through previous research, clinical cases, and external cases. All imaging sets will be categorized as negative, biopsy proven benign, or biopsy proven malignant.

### 1.1.4 Reader Study:

Imaging sets of CESM and MRI will be randomly selected from the three groups of cases (negative, biopsy proven benign, and biopsy proven malignant) to create an enriched reader set for retrospective review with a proportion of cases as outlined in Figure 1 of the schema, reproduced below. 88 negative/benign cases and 44 cancer cases will be randomly selected.

[figure not shown]

Figure 1. Reader Study. Prospectively acquired imaging sets will be added to existing cases for the case collection. Types of cases and the number of cases to be recruited are presented. Cases to be used for the reader study are shaded green.

*Radiologist Readers:* 13 radiologists will participate in this study. Radiologists who are in fellowship training for breast imaging or those who are MQSA certified to interpret mammography exams are eligible as long as they can commit to interpret all imaging within the study case set.

Readers that are also co-investigators will not be paid, as this will present a conflict of interest. Only readers who are not co-investigators will be paid. It is appropriate to pay them as the reader study will take a significant amount of their time and we will not be able to recruit readers without compensating them appropriately.

*Recruitment:* We intend to recruit internal DF/HCC radiologist readers. We will only recruit non-DF/HCC readers if the number of internal readers identified does not suffice. In the event that external readers are needed, we will execute a Data Usage Agreement prior to their participation on the study. To identify radiologist readers, an email will be sent out to Breast Imaging radiologists at academic centers in Boston. This email will describe the study and commitment required of the readers. Readers will be provided an honorarium for participation or will be authors on papers generated. Verbal or email affirmation of an interest in participation to the research coordinator will serve as informed consent. No documentation of informed consent will be provided for this study as this study presents no more than minimal risk and the performance of imaging interpretation is within their scope of clinical practice for which informed consent would not routinely be necessary. The study coordinator will schedule time for the radiologist readers to complete the required case reads for the reader study. Their name, experience reading breast MRI, and experience reading CESM will be collected at the time of enrollment at which time they will be given a reader ID number. The readers' interpretations of the imaging sets will be performed anonymously using their reader ID numbers.

*Training Cases:* All readers who have interpreted less than 30 CESM cases, either as part of prior research or clinical practice, will receive a background presentation on CESM and will complete a training set of 30 CESM cases prior to beginning the reader study. These cases will include cancer and non-cancer cases. Answers will be provided for these cases prior to the start of the formal reader study. In addition, all readers will be trained on the conduct of the study to include 5 cases of how to interpret and record their interpretations.

*Image Interpretation:* Each of the 132 cases comprising the study set will have both a CESM and MRI. Half of the readers will read the 132 CESM cases first (called the CESM study session) and then will read the 132 breast MRI cases (the MRI study session). The other half will do the reverse, and will interpret the MRI cases first followed by the CESM cases. There will be a month wash-out period between the two sessions. Each reader will independently review and score each of the images.

A. CESM session: - Review and score the low energy images (these images are equal to conventional 2D mammographic images); this will be the MG score

- Then review and score the low energy images combined with the subtraction images (this is the CESM exam); this will be the CESM score.

B. MRI session: - Review and score the abbreviated MRI sequences (these are a subset of the full protocol); this will be the abMRI score. - Then review and score the complete MRI exam; this will be the MRI score.

The order of image presentation per reader is randomized. Half will complete the CESM session first and the other half will complete the MRI session first. Cases will be randomized and counterbalanced to account for learning, experience, and fatigue that occur during reader studies. Readers and study assistants will be blinded to the details of the investigational site, subject history, previous mammography images, and previous clinical results. The radiologist reader will provide a forced BIRADS score of 1,2,3,4a, 4b, 4c, or 5 defined, respectively, as negative, benign findings, probably benign findings, low suspicion for malignancy, moderate suspicion for malignancy, high suspicion for malignancy, and highly suggestive of malignancy associated with probability of malignancy of (0%), (0%), (::=::2%), (>2% to ::=;10%), (>10% to ::=;50%), (>50% to <95%), and (95%), respectively. Each case will also be scored for confidence in diagnosis on a 5-point Likert scale using strongly confident, confident, neutral, not confident, and strongly not confident. This will be the confidence score. Readers will report their interpretations into RedCap database using reader ID numbers and the results will be analyzed anonymously.

The reader study will take place after all the imaging studies have been acquired and reported. Consensus will not be necessary for the reader study. We will be evaluating individual and group ROC curves.

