# 12.1 Study Design/Endpoints

Exams will be interpreted by 13 radiologist readers. Each reader will score each CESM and MRI exam according to the Breast Imaging-Reporting and Data System (BI-RADS), ranging from 1-5. The score used will correspond to the most suspicious finding in the study. The primary outcome will be whether the exam is benign or malignant. BI-RADS scores 1, 2, and 3 associated with the corresponding categories of negative, benign findings, and probably benign findings will be negative (benign). BI-RADS scores 4 and 5 associated with the corresponding categories of suspicious for malignancy will be positive (malignant).

Positive truth will be determined by histopathology confirming malignant pathology. If a woman has had both a percutaneous breast biopsy and surgical excision, the worst pathology will be considered for analysis.

Negative truth will be considered for all cases categorized as negative or biopsy proven benign. All cases will require two-year follow-up to confirm the absence of malignancy. The follow-up will take the form of any documentation of the woman's health to include the online medical record (OMR) or imaging archival system, or direct communication with her.

At the time of the reader study, there may be cases classified as negative that have not had complete follow-up since their initial CESM and MRI exams. These cases will be reevaluated after the reader study has been completed to confirm whether the cases represent false negatives. This will be accounted for in the subsequent analysis. Given that the false negative rate of MRI is low and approximates 3%, it is unlikely that this will impact the analysis significantly (17).

We will compare the BI-RADS score of CESM and MRI with the final outcome of negative or positive truth to determine the area under the curve for each technology for ROC analysis.

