# 12.2 Sample Size, Accrual Rate and Study Duration

Objective 1: To compare the diagnostic accuracy of CESM with breast MRI for detection of breast cancer.

Area under the ROC curve (AUC) of CESM and MRI will be calculated for each of the 13 readers and compared with Delong & Delong (1988)'s method within each reader. The reader average AUC will be calculated for each modality and the difference between the modalities and its associated 95% confidence interval will be calculated using Obuchowski's method.

Objective 2/3: To compare the diagnostic accuracy of CESM with abbreviated MRI for detection of breast cancer.

Area under the ROC curve (AUC) of CESM and abbreviated MRI will be calculated for each of the 10 readers and compared with Delong & Delong (1988)'s method within each reader. The reader average AUC will be calculated for each modality and the difference between the modalities and its associated 95% confidence interval will be calculated using Obuchowski's method.

Objective 4: Descriptive statistics will be used to evaluate patient responses to the survey

*Sample Size Justification:* The analysis aims to test the non-inferiority of CESM when compared to MRI by establishing no loss of value in the ROC AUC. The null hypothesis is HO: (Reader average AUCCESM- reader average AUCMRI) :S -0.05 versus the alternative HA: (reader average AUCCESM-reader average AUCMRI) > -0.05. The test is based on a 2-sided 95% confidence interval on the difference between the reader average AUCs. The ROC power and the sample size calculations are based on the methods of Zhou, Obuchowski and McClish.

Assuming the average AUC of the two modalities is 0.83, the correlation for same reader, different modalities is 0.47, correlation for different reader, same modality is 0.44, correlation for different reader, different modalities is 0.4 and correlation for group of readers, different modalities is 0.8. The interobserver variability is 0.002 and the intraobserver variability is 0.0004. The pooled readings from 13 readers on 44 cancer cases and 88 non-cancer cases will have at least 80% power to reject the null hypothesis that (AUCCESM - AUCMRI) S -0.05 with a 95% 2 sided confidence interval on the difference. The lower end of the confidence interval for the difference (AUCCESM - AUCMRI) must be greater than -0.05 to accept the alternative hypothesis of non-inferiority.

Accrual Targets for Prospective Recruitment					
Ethnic Category	Sex/Gender				

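### Session order is randomised by reader but left out of the 12.2 analysis, so a common session effect would make the non-inferiority test conservative and cost some power

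*Combined protocol and SAP*

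**What the plan says.** Section 1.1.4 (Reader Study) sets the number of readers: "13 radiologists will participate in this study". Section 12.1 agrees: "Exams will be interpreted by 13 radiologist readers".

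On order, 1.1.4 says "Half of the readers will read the 132 CESM cases first (called the CESM study session"), and then "The other half will do the reverse, and will interpret the MRI cases first followed by the CESM cases". It adds "There will be a month wash-out period between the two sessions". Order is randomised per reader. The stated purpose of the arrangement is control of learning and similar effects: "Cases will be randomized and counterbalanced to account for learning, experience, and fatigue that occur during reader studies". Section 10.1 repeats the half-and-half arrangement. No section says how 13 readers are to be divided.

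The analysis is in 12.2. AUCs are compared within each reader by DeLong's method, and then "The reader average AUC will be calculated for each modality and the difference between the modalities and its associated 95% confidence interval" is obtained by Obuchowski's method. Non-inferiority requires the lower limit to exceed -0.05. Sections 12.5 and 12.6 only refer back to 12.1 and 12.2, and 12.3 lists no stratification factors. No order or session term, and no sensitivity analysis by order, appears anywhere.

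For the comparison with abbreviated MRI, 12.2 gives a different reader count: "Area under the ROC curve (AUC) of CESM and abbreviated MRI will be calculated for each of the 10 readers".

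**The concern.** The plan names learning and fatigue as threats and randomises order to deal with them, but the analysis then drops the factor that was randomised. Counterbalancing cancels a session effect in the average. It does not take that effect out of the spread between readers.

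Suppose AUC in the second session exceeds AUC in the first by g for both modalities. A CESM-first reader then shows a CESM-MRI difference of (true difference - g), and an MRI-first reader shows (true difference + g). An analysis that ignores order treats this gap of 2g as genuine variation between readers in how the modalities compare. The extra variance widens the one interval that decides the primary objective.

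Some session effect is plausible. Fellows in training may read, readers new to CESM are admitted after a training set, and the two sessions span months 17 to 22 of the study calendar.

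**Working it through.** **Inputs from the documents (12.2 unless stated).** J = 13 readers; 44 cancer and 88 non-cancer cases; margin -0.05; two-sided 95% interval; average AUC 0.83; r1 = 0.47, r2 = 0.44, r3 = 0.40, rb = 0.8; inter- and intraobserver variability 0.002 and 0.0004; stated power at least 80%. **Assumed:** g = 0.01 to 0.03 AUC, a true difference of zero, and an Obuchowski interval that uses the observed reader-by-modality mean square.

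**Step 1: the plan's own power.** Obuchowski's formula is

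Var = (2/J){sb²(1 - rb) + sw² + Vc[(1 - r1) + (J - 1)(r2 - r3)]}.

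With 0.002 and 0.0004 read as variances and a binormal Vc = 0.00199:

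Var = (2/13){0.0004 + 0.0004 + 0.00199 × 1.01} = 0.000433, so SE = 0.0208.

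Power = Φ(0.05/0.0208 - 1.96) = 67.1%. A Hanley-McNeil Vc of 0.00170 gives 71.9%. With the two figures read as standard deviations, the binormal version gives 81.1%. The plan does not say which reading it used, so the 80% is not called wrong here. The main calculation takes it at face value:

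SE0 = 0.05/(1.960 + 0.842) = 0.01785.

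**Step 2: added variance.** With a 7/6 split, the expected sample variance of the 13 reader differences rises by

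g² × (4 × 7 × 6/169) × (13/12) = 1.077g².

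The variance of the mean difference therefore rises by 1.077g²/13 = 0.0828g².

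**Step 3: effect on the interval and power.** SE1 = √(SE0² + 0.0828g²). Power is shown two ways: Φ(0.05/SE1 - 1.96), and with the estimator's true SE held at SE0, Φ((0.05 - 1.96 × SE1)/SE0). Neither column includes the bias of Step 4.

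| g (assumed) | SE1 | Interval wider by | Power, first way | Power, second way |
|---|---|---|---|---|
| 0 | 0.01785 | 0 | 80% | 80% |
| 0.01 | 0.01808 | 1.3% | 79.0% | 79.3% |
| 0.02 | 0.01875 | 5.1% | 76.0% | 77.1% |
| 0.03 | 0.01983 | 11.1% | 71.3% | 73.4% |

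Starting from SE = 0.0208 instead, the widening is 1.0%, 3.8% and 8.3%.

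**Step 4: what the odd number of readers adds.** The bias of the simple mean is g(7 - 6)/13 = g/13: 0.0008, 0.0015 and 0.0023, or 1.5%, 3.1% and 4.6% of the margin. Its sign depends on which order gets seven readers, which is not stated. With an exact half split the bias is zero, but the added variance is g²/(J - 1). For 12 readers that is g²/11 = 0.0909g², against 0.0828g² here.

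**Step 5: error rate at the margin.** With the widened interval and the bias in the direction that favours CESM, the chance of a false non-inferiority claim is 1 - Φ((1.96 × SE1 - g/13)/SE0): 2.6%, 2.4% and 2.0% for the three values of g, against a nominal 2.5%. Without the bias it is 2.4%, 2.0% and 1.5%.

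**Step 6: what stratifying by order does.** The equally weighted mean of the two order groups is ½[(δ - g) + (δ + g)] = δ, so a common g drops out for any group sizes. The weighting costs (1/7 + 1/6)/4 = 0.07738 against 1/13 = 0.07692, a factor of 1.006 on the between-reader part of the variance. Degrees of freedom go from 12 to 11. If a t quantile is used, it rises from 2.179 to 2.201, about 1%.

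**The case against.** The strongest reply is that the design already handles learning. Order is randomised, cases are counterbalanced, sessions are a month apart, readers with fewer than 30 CESM reads complete 30 training cases with answers, and all readers do five procedural cases. The same women are read twice, but on different modalities. All this stands and argues for a small g. It does not make g zero, and the documents give no value. At g = 0.01 the widening of 1.3% is about what the adjustment itself costs under a t quantile, so the gain appears only at larger values.

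A reader might infer that 13 readers break the crossover and bias the primary comparison. The documents do not support that. A 7/6 split cancels 12/13 of a common session effect, and what remains is trivial beside 0.05. The widening comes from the missing order term, not from the odd count.

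A reader might also infer that the primary test is invalid. It is not. The widening makes non-inferiority harder to claim, and the error rate stays at or below about 2.6%.

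Learning that differs by modality is a separate matter. With assumed second-session gains of 0.03 for CESM and 0.01 for MRI, the bias is (0.03 - 0.01)/2 = 0.010 with equal halves, and 0.0085 or 0.0115 at 7/6. An even split does not remove it, and nor does an order term: 0.010 remains after equal weighting.

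**Conclusion.** The point holds as a matter of efficiency. A factor that the trial randomises is left in the error term of its primary test. For an assumed common session effect of 0.01 to 0.03 AUC, the interval is about 1% to 11% wider, and power falls from the plan's 80% to between about 79% and 71-73%. The consequence is a conservative test, not a false claim of non-inferiority. The 7/6 split is a wording gap with a bias of 0.0023 or less.

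These sizes rest on three assumptions: the value of g, which is not in the documents; an interval built on observed reader-by-modality variation (if fixed planning values were used instead, the widening would not arise); and the SE implied by the stated power, which Step 1 reproduces under some readings of the inputs but not others.

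**What to change.** In 12.2, prespecify session order in the primary reader-average analysis:

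- Estimate the CESM-MRI difference as the equally weighted mean of the CESM-first and MRI-first group differences.
- Compute the reader-by-modality mean square within order groups (13 - 2 = 11 df).
- Keep the case-covariance terms of Obuchowski's variance. At the plan's correlations and the binormal Vc they contribute 2 × 0.00199 × 0.04 = 0.00016 of 0.00043, about 37%, so dropping them would make the interval too narrow.
- Report the estimated session effect.

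In 1.1.4 and 10.1, replace the half split with a randomised 7/6 allocation and say how the order with seven readers is chosen.

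Apply the same analysis to CESM against abbreviated MRI, but first reconcile the 10 readers stated there in 12.2 with the 13 stated elsewhere. Ten would divide 5/5.

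The cost is SAP wording and one extra term, with no new readers, cases or images. If there is no session effect, the price is one degree of freedom and at most about 0.6% more variance. The change should be made before any results are seen, because an order adjustment added later to a limit near -0.05 would look data-driven. It does not protect against modality-specific learning, and the report should say so.
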